9.1.5 Adverse Events (AEs)

An AE is defined as any untoward medical occurrence associated with the use of a study drug in humans, whether considered drug related. An AE can, therefore, be any unfavorable and unintended sign (including clinically significant abnormal laboratory finding), symptom or disease temporally associated with the use of the study drug, whether related to the investigational product.

AEs will be monitored throughout the study. Patients will be instructed to inform the Investigator and/or study staff of any AEs. At each visit, patients will be asked about AEs in a non-specific manner using open-ended questions so as not to bias the response (e.g., How have you been since the last visit?). Specific inquiry regarding reported AEs will be conducted when applicable. All AEs will be documented and recorded in the patient's eCRF.

Any patient who has an AE (serious or non-serious) will be evaluated by the Investigator and treated and followed until the symptom(s) return to normal or to clinically acceptable levels, as judged by the Investigator. A physician, either at clinical site, or at a nearby hospital emergency room, will administer treatment for any serious AEs (SAEs), if necessary. When appropriate, medical tests and examinations will be performed to document resolution of event(s).

9.1.5.1 Reporting

Only AEs that occur during or following study treatment with the study drug will be reported in the AE section of the eCRF. Events recorded prior to study treatment with the drug will be reported in the Medical History section of the eCRF. All AEs occurring during the study will be individually recorded in the eCRF. Any condition present prior to administration of study drug and that worsens after administration of study drug should be reported as an AE. Information regarding the onset, duration, severity, action taken, outcome, and relationship to study drug will be recorded.

New or worsening abnormal laboratory values and/or vital signs are to be recorded as AEs if they are considered to be of clinical significance by the Investigator or meet the criteria of an SAE as described in Section 9.1.6. Unless a diagnosis is available, signs and symptoms must be reported as individual AEs in the eCRF; a diagnosis is preferred.

The severity of an AE will be designated as mild, moderate or severe. The term “severe” is used to describe the intensity of an AE; the event itself, however, may be of relatively minor clinical significance (e.g., ‘severe’ upper respiratory infection). Severity is not the same as “serious”. Seriousness of AEs is based on the outcome/action of an AE. (See Section 9.1.6.)

The relationship of the AE to the study treatment should be determined by the Investigator and will be based on the following two definitions:

Not related: The AE is judged to not be associated with the study drug, and is attributable to another cause.

Related: A causal relationship between the AE and the study drug is a reasonable possibility, i.e., there is evidence (e.g., dechallenge/rechallenge) or other clinical arguments to suggest a causal relationship between the AE and study treatment.

9.1.6 Serious Adverse Events (SAEs)

An SAE is defined as any untoward medical occurrence that,

- Results in death
- Is in the opinion of the Investigator immediately life threatening (i.e., the patient is at immediate risk of death; it does not include a reaction that, had it occurred in a more severe form, might have caused death)
- Requires inpatient hospitalization or results in prolongation of an existing hospitalization
- Results in persistent or significant disability or incapacity
- Is a congenital anomaly or birth defect
- Is an important medical event that may not be immediately life-threatening, result in death, or require hospitalization, but based on appropriate medical judgment, it jeopardizes the patient, or may require medical or surgical intervention to prevent one of the outcomes listed.

The Investigator should institute any clinically necessary supplementary investigation of SAE information. In the case of patient death, any post-mortem findings/reports will be requested.

9.1.6.1 Reporting of SAEs

All SAEs, as defined in Section 9.1.6, regardless of causal relationship, must be reported to the Sponsor or designee within 24 hours of the Investigator becoming aware of the event. As soon as the Investigator becomes aware of an AE that meets the criteria for an SAE, the SAE should be documented to the extent that information is available.

SAEs will be recorded from the time of informed consent/assent until the end of the study. If, in the opinion of the Investigator, an SAE occurring outside the specified time window (i.e., following patient completion or terminations of the study) is deemed to be drug-related, the event should be reported with 24 hours.

SAEs must be recorded on an SAE form. The minimum information required for SAE reporting includes the identity of the PI, site number, patient number, event description, SAE term(s), reason why the event is considered serious (i.e., the seriousness criteria), and PI's assessment of the relationship of the event to study drug. Additional SAE information including medications or other therapeutic measures used to treat the event, and the outcome/resolution of the event should also be recorded on the SAE form.

In all cases, the Investigator should continue to monitor the clinical situation and report all material facts relating to the progression or outcome of the SAE. The Investigator may be required to provide supplementary information as requested by the Sponsor or its designee.

When reporting SAEs, the following additional points should be considered:

- Although signs, symptoms, and tests that support the diagnosis of an SAE should be provided, the Investigator should report the diagnosis or syndrome as the SAE term.
- Death should not be reported as an SAE, but as an outcome of a specific SAE (unless the event preceding the death is unknown). If an autopsy was performed, the autopsy report should be provided.

Although most hospitalizations necessitate reporting of an SAE, some hospitalizations do not:

- Hospitalization for elective or previously scheduled surgery, or for a procedure for a pre-existing condition that has not worsened after administration of study drug (e.g., a previously scheduled ventral hernia repair). SAEs must, however, be reported for any surgical or procedural complication that lead to prolongation of the hospitalization.
- Events that result in hospital stays for observation of <24 hours and that do not require a therapeutic intervention/treatment (e.g., an emergency room visit for hematuria that results in a diagnosis of cystitis and discharge to home on oral antibiotics).

The Sponsor will process and evaluate all SAEs as soon as the reports are received. For each SAE received, the Sponsor will determine whether the criteria for expedited reporting to relevant regulatory authorities have been met.

The Sponsor will assess the likelihood that each SAE is related to study treatment, with the current Investigator's Brochure used as the reference document to assess expectedness of the event to study drug.

9.1.7 Adverse Events of Special Interest (AESI)

AESIs in this study include:

- Anaphylactic reactions or acute allergic reactions that require immediate treatment
- Malignancies (excluding non-melanoma skin cancers).

All AEs must be reported to the sponsor and designee within 24 hours of identification.

9.1.8 Pregnancy

In the instance that a patient becomes pregnant during participation in the study, the patient must be withdrawn from study drug but may continue study participation. The Investigator must perform medical assessments as clinically indicated and continue to follow the patient for ≥ 4 weeks after delivery, at a minimum. Details for both the mother and baby must be obtained.

Although pregnancy is not itself an AE or SAE, maternal/fetal complications or abnormalities will be recorded as AEs or SAEs, as appropriate.

The Investigator must complete a study-specific Pregnancy Form upon confirmation of a pregnancy. Pregnancy reporting forms will be provided to the site.

10 STUDY DISCONTINUATIONS

10.1 Study Termination

The Sponsor has the right to terminate or to stop the study at any time. Should the study be terminated, the decision and reason will be communicated in writing by the Sponsor to the Investigator and request that all patients be discontinued. Should this be necessary, patients should be scheduled for an Early-termination visit (Section 7.4).

The entire study will be stopped if:

- Evidence has emerged that, in the collective opinion of the Investigators at each site with the concurrence of the Sponsor, or the sole opinion of the Sponsor, continuation of the study is unnecessary or unethical
- The stated objectives of the study are achieved
- The Sponsor discontinues the development of the study drug

If the study is terminated by the Sponsor, all data available for the patient at the time of discontinuation must be recorded in the patient's records and the eCRF.

10.2 Early Termination of Study Patients

The Investigator will make every reasonable effort to keep each patient in the study. However, patients may terminate or be terminated early from the study for the following reasons:

- Voluntarily withdrawal of consent to participate in the study participation, at any time
- Adverse event, laboratory abnormality or inter-current illness which, in the opinion of the Investigator, indicates that continued treatment and/or participation in the study is not in the best interest of the patient
- Serious protocol violation, persistent non-compliance or requirement for medication or procedure prohibited by the protocol
- Lost to follow-up

Patients who are terminated early from study will have an Early-Termination visit scheduled (Section 7.4) as soon as possible. All information, including the reason for early discontinuation will be recorded in the patient's study records and in the eCRF.

Before a patient can be terminated early due to loss of follow-up, the Investigator must show documented attempts to contact the patient regarding study participation on two separate occasions (telephone contact) followed by a certified letter of contact.

Prior to discontinuing a patient from study participation, the Investigator will discuss his/her intentions with the Sponsor Medical Monitor or designee.

10.3 Study-Drug Discontinuation

Study drug must be discontinued for patients who experience the following:

- Inter-current illness that would, in the judgment of the Investigator, affect assessments of clinical status to a significant degree
- Treatment related AEs that are clinically significant, deemed persistent, in the judgment of the Investigator
- Unacceptable toxicity
- Pregnancy

Patients who discontinue study drug permanently during study participation must be scheduled for an Early-termination visit (Section 7.4).

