7.4 Visit Day 113 (Week 16) (+/- 3 Day) (End-of-Treatment/Early-Termination Visit)

Patients who discontinue the study early for any reason should have these assessments performed at their early-termination visit. The reason for early termination must be recorded in the patient’s records and the eCRF.

- Confirm emollient use.
- Perform a complete physical examination, including weight.
- Measure vital signs.
- Collect concomitant medication and procedure/therapy information.
- Review and record AEs.
- Collect a 12-lead ECG.
- Draw blood samples for laboratory tests (hematology and chemistry).
- Draw a blood sample for PK and ADA testing.
- Collect urine for urinalysis and urine pregnancy test (WOCBP only).

- Review compliance report on the electronic tablet for the daily assessments (pruritus NRS, including a global impression of change for itching; sleep-loss NRS; and ADIQ).
- Collect electronic tablets and download any remaining data on device.
- Complete the following assessments:
 - Investigator’s Global Assessment (IGA)
 - Eczema Area and Severity Index (EASI)
 - Body Surface Area (BSA)
 - Patient-Oriented Eczema Measure (POEM)
 - Dermatology Life Quality Index (DLQI)
 - Hospital Anxiety and Depression Scale (HADS)
 - Global Assessment of Change for AD.
- Remind the patient to apply an emollient twice daily.
- Schedule next visit.

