6.1.3 Visit Windowing

Efficacy data will be summarized based on nominal visit indications with the exception of data captured at early termination and unscheduled visits. Efficacy data from early termination and unscheduled visits will be summarized based on mapped visit values. The analysis windows for early termination and unscheduled visits are presented in the following table.

Analysis Windows for Efficacy Assessments

Scheduled Visit	Target Study Day	Window (Days)
Week 2	15	9 to 22
Week 4	29	23 to 36
Week 6	43	37 to 50
Week 8	57	51 to 64
Week 10	71	65 to 78
Week 12	85	79 to 92
Week 14	99	93 to 106
Week 16	113	107 to 127
Week 20	141	128 to 158
Week 24	169	159 to 197
Week 32	225	198 to 239

Efficacy data collected prior to study day 9 for early termination and unscheduled visits will not be analyzed, with the exception of those identified as baseline values. Efficacy data collected at early termination and unscheduled visits after study day 239 will not be included in analyses.

The definition for the study day included in each study window is defined below:

Study Day prior to Day 1 = Visit Date – Day 1 Date

Study Day on or after Day 1 = Visit Date – Day 1 Date + 1

If an assessment's mapped visit is a visit at which the subject has data from a scheduled visit present, or if no analyses are planned for the assessment at the mapped visit, the data collected at the early termination or unscheduled visit will not be included in analyses.

In the event of multiple values from unscheduled or early termination assessments within an analysis window, the value closest to the scheduled visit target study day will be used for analyses. If two values tie as closest to the time point (for example, one value is before and the other value is after the time point), then the later value will be selected.

Safety data will be summarized based on nominal visit indications. Data captured at early termination will be assigned an Analysis Window visit based on the "Analysis Windows for Efficacy Assessments" above. Unscheduled visits will not be summarized.

Data collected at all visits will be included in the data listings with visit presented as reported by the site, except for subject reported electronic diary data. Subject reported electronic diary data listings will be presented with analysis visit, since there is no site reported visit.

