6.13.3.2 Repeated Measures Analyses on Observed Data

The second set of sensitivity analyses will be performed on observed data. The primary endpoint of percent change from baseline in EASI score at Week 16 will be analyzed with a repeated measures ANCOVA, with treatment, visit (Weeks 4, 8, 12, and 16), and treatment by visit interaction as factors, and a covariate of baseline EASI score.

The two dichotomized secondary endpoints of IGA and EASI75 at Week 16 will each be analyzed with a repeated measures logistic regression model (generalized estimating equations), with the dichotomized endpoint as the dependent variable and treatment, visit (Weeks 4, 8, 12, and 16), and treatment by visit interaction as factors.

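### Protocol 10.3 sends every permanent stopper to the early-termination visit while 9.1.8 lets a pregnant patient stay in the study, and no Week 16 EASI is explicitly planned after that visit

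*Protocol*

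**What the plan says.** **Stopping drug and leaving the study.** Protocol 10.3 lists the reasons for which drug must be stopped, pregnancy among them, and ends: "Patients who discontinue study drug permanently during study participation must be scheduled for an Early-termination visit (Section 7.4". Section 7.4, to which it points, says whom the visit is for: "Patients who discontinue the study early for any reason should have these assessments performed at their early-termination visit". Protocol 10.2, on patients who leave the study, sends them to the same 7.4 visit. Protocol 9.1.8 says that after a pregnancy "the patient must be withdrawn from study drug but may continue study participation". Section 10.2 also states: "The Investigator will make every reasonable effort to keep each patient in the study".

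**Use of the early-termination EASI.** EASI and IGA are both assessed at the 7.4 visit. SAP 6.1.3 then says: "Efficacy data from early termination and unscheduled visits will be summarized based on mapped visit values". The Week 16 window is Days 107 to 127. Early-termination efficacy data from before Day 9 are not analysed. After that, "if no analyses are planned for the assessment at the mapped visit, the data collected at the early termination or unscheduled visit" are left out, and the same holds if a scheduled value already exists at the mapped visit. The repeated-measures analysis of EASI uses "visit (Weeks 4, 8, 12, and 16"), which matches the EASI visits in Protocol Appendix 1 during treatment.

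**Missing Week 16 values.** Protocol 11.1 and SAP 6.1.6 impute missing EASI and IGA in the mITT population by MCMC multiple imputation, separately in each arm. Both state that the method needs no missing-at-random assumption. Non-responder imputation (SAP 6.1.7, 6.13.3.1 and 6.13.3.3) is set out for IGA and EASI75.

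**The concern.** A site reading 10.3 with 7.4 could conclude that a patient who stops drug has reached the end of efficacy assessment. A site reading 9.1.8, or the retention sentence in 10.2, could conclude the opposite. Sites may therefore differ in whether they bring stoppers back at Week 16.

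The data at stake are the primary endpoint values of those who stop. The reasons in 10.3 include intercurrent illness that affects assessment, persistent treatment-related adverse events and unacceptable toxicity, so stopping may well be related to outcome. If these patients have no Week 16 EASI, their values are filled in from a model fitted to their own arm, where most patients are presumably still on drug, and no observed post-discontinuation value is available to check the result.

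**Working it through.** There is no planned figure to reproduce. Protocol 11.9 and SAP 7 base the sample size on clinical considerations and give no dropout rate, SD or effect. The allocation agrees: 275 × 3/11 = 75 per active arm and 275 × 2/11 = 50 on placebo.

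**1. The passages side by side**

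| Section | What triggers it | What follows |
|---|---|---|
| Protocol 10.2 | Leaving the study | 7.4 visit |
| Protocol 10.3 | Permanent stop of drug, including pregnancy | 7.4 visit, no exception |
| Protocol 7.4 | Leaving the study early | Week 16 assessments done at that visit, electronic tablet collected |
| Protocol 9.1.8 | Pregnancy | Off drug, may stay in the study |

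Sections 10.3 and 9.1.8 address the same pregnant patient. The first sends her to a visit that 7.4 reserves for those leaving; the second lets her stay. Neither these sections nor Appendix 1 says that a stopper attends Week 16 after the early-termination visit.

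**2. When the early-termination EASI is used** (SAP 6.1.3 windows; EASI visits at Weeks 4, 8, 12 and 16)

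- Days 2 to 106 inclusive: 106 − 2 + 1 = 105 days.
- Days 2 to 8, before the first window: 7 days, not analysed.
- Week 2 (Days 9–22), Week 6 (37–50), Week 10 (65–78) and Week 14 (93–106): 4 × 14 = 56 days. No EASI is planned at these visits, so the value is not analysed.
- Not analysed: 7 + 56 = 63 of 105 days, or 60%.
- Week 4 (23–36), Week 8 (51–64) and Week 12 (79–92): 3 × 14 = 42 days. The value is used only if no scheduled value exists there.
- Days 107 to 127: the value counts as Week 16.

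The unused days include Days 93 to 106, the window around the last dosing visit (Day 99). This is a count of calendar days, not a probability: stopping need not be spread evenly over time.

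**3. How many Week 16 values would be imputed**

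With d the share stopping before Day 107 without a later Week 16 assessment (assumed, equal in all arms), the number is 275 × d:

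| d (assumed) | Per active arm (75d) | Placebo (50d) | Total (275d) |
|---|---|---|---|
| 10% | 7.5 | 5 | 27.5, about 28 |
| 20% | 15 | 10 | 55 |

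**4. What that could do to the estimate**

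Let g be the mean gap in an arm between the true and imputed Week 16 percent change among stoppers. The arm mean is off by d × g, that is 0.10g to 0.20g over the range above. The contrast of an active arm with placebo is off by (d × g in the active arm) − (d × g in placebo). It is zero if the two products are equal. The documents give neither d nor g, so no figure for bias can be derived.

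**5. Is the imputation tested?**

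Both documents describe the MCMC model as multivariate normal. In its standard form that imputation does assume missing at random, and fitting it separately by arm does not remove the assumption. The sensitivity analysis that SAP 6.13.3.2 gives for percent change in EASI is a repeated-measures ANCOVA on observed data, which relies on the same kind of assumption.

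**The case against.** The strongest reply is that 10.3 requires a visit to be scheduled and nowhere says that the patient leaves the study. The protocol has separate sections for the two events, 10.2 favours retention, the title of 7.4 also covers end of treatment, and its last step is to schedule another visit. Appendix 1 does not excuse off-drug patients from Week 16. A reader might infer that everyone who stops drug is terminated from the study; the documents do not say so. This part of the reply stands. What remains is that the text can be read both ways and that no sentence plans Week 16 for a stopper. The closing step of 7.4 does not settle it, because the same list serves patients who complete Week 16 and go on to follow-up.

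A reader might also infer that the primary result as a whole rests on imputed values. It does not. Only patients without an EASI on Days 107 to 127 are imputed, their own earlier visits may inform the imputation, and an early-termination value at Week 4, 8 or 12 can contribute where no scheduled value exists.

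Other parts are handled. For EASI75 and IGA, one analysis counts missing as non-response, and another counts rescue use or early stop of treatment as non-response. The per-protocol analyses carry the last value forward, but that population largely requires attendance at Week 16; the exception is patients who leave for a treatment-related adverse event. Neither route tests the mITT analysis of percent change in EASI.

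Finally, following patients after they stop drug answers a particular question, the effect regardless of stopping, and this is a Phase 2b study in which p-values are descriptive aids. That is a fair reason to ask for a sensitivity analysis and not for a new primary analysis.

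**Conclusion.** The point holds in limited form, as a cheap improvement. Protocol 10.3 with 7.4 conflicts with 9.1.8, and the passages must be reconciled; I take no view on which clinical rule should apply. As written, a stopper whose early-termination visit falls before Day 107 has no explicitly planned Week 16 EASI or IGA, and the early-termination EASI goes unused on 63 of 105 possible days. The missing Week 16 value is imputed within arm, without a readable sensitivity analysis of percent change in EASI that departs from missing at random.

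The size is unknown. The figure of 28–55 imputed values out of 275 assumes 10–20% stopping before Day 107 in every arm and no later Week 16 assessment. A reader might go on to put a number of percentage points on the bias. The documents support none: they give no stopping rate and no gap between stoppers and others, and bias in the contrast depends on how the arms differ.

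One reservation applies. In the copy reviewed, the SAP text breaks off in 6.12 and resumes within 6.13.2, so 6.13.1 on the primary analysis could not be read. It may say more about stoppers.

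**What to change.** 1. Reconcile Protocol 9.1.8, 7.4 and 10.3 so that they agree on whether a patient who has stopped drug is still in the study.
2. Leave the rules on when drug is stopped as they are. Record drug discontinuation and study withdrawal as separate events, each with its own date and reason.
3. Ask patients who stop drug and have not withdrawn consent to attend the already scheduled Week 16 visit for EASI and IGA, and say so in 7.4 and Appendix 1.
4. Add to SAP 6.13.3 a sensitivity analysis of percent change in EASI that includes these post-discontinuation values.

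The cost is protocol and SAP wording, one existing visit for the patients who stop, and a little more analysis. No new staff or procedure is needed. It will not recover patients who withdraw consent or are lost to follow-up. Protocol 6.10 separately discontinues from the study those who need systemic therapy for AD; the reconciled text should state whether the Week 16 request covers them.
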